Presently, treatment for insomnia (in the case of cognitive behavioral treatment for insomnia [CBT-I]) focuses on limiting time in bed to reduce night-time wakefulness, thereby improving sleep continuity and daytime performance. The proposed project approaches insomnia treatment differently: the same outcomes may be achieved by enhancing and/or extending wakefulness during the day. The current proposal will test whether enhancing daytime wakefulness using a wake-promoting medication, solriamfetol, can improve sleep continuity and daytime performance, both as a stand-alone and in combination with CBT-I.

The current pharmacological approach for the treatment of insomnia is largely sedative medications, which promote sleep and have some benefit, but considerably limited efficacy compared to cognitive behavioral treatment for insomnia (CBT-I). Part of the mechanism of action for CBT-I is that over the course of 2-6 weeks of behavioral treatment, time in bed is severely limited, which has the intended outcome of increasing homeostatic sleep drive and thereby reducing night-time wakefulness. The current unknown is whether implementing this mechanism via wake-promoting medication can achieve efficacious outcomes. It is expected (given a common mechanism [wake extension]) that both CBT-I and treatment with solriamfetol [SFTRL] will improve sleep continuity, and that such effects will potentially be additive. Preliminary work by our group with another wake promoting medication suggests that such outcomes are feasible (PMID: 15283007). If successful, this unique treatment approach may provide an important alternative for patients that do not tolerate sleep restriction during CBT-I or for whom the transient iatrogenic sleepiness of CBT-I represents an unacceptable risk (e.g., surgeons, pilots, etc.).

2. Name and Description of the Investigational Product

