2.1 Nonclinical and Clinical Data To Date

The use of solriamfetol to treat EDS has been evaluated and extensively profiled in the literature. Given the shared EDS phenotype between narcolepsy, OSA, and insomnia, such data support that solriamfetol may be useful in those patients who cannot or do not tolerate the iatrogenic effects of sleepiness in CBT-I. Three such studies are listed below:

Krystal, A. D., Benca, R. M., Rosenberg, R., Schweitzer, P. K., Malhotra, A., Babson, K., ... & Strohl, K. P. (2022). Solriamfetol treatment of excessive daytime sleepiness in participants with narcolepsy or obstructive sleep apnea with a history of depression. *Journal of psychiatric research*, 155, 202-210.

Servid, S. (2012). New Drug Evaluation: solriamfetol tablets, oral.

2.2 Human Pharmacokinetics The time to peak levels of solriamfetol is about 2 hours (range 1.25–3.0 hours). Solriamfetol is minimally metabolized in humans. Its elimination half-life is about 7.1 hours.

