5.6 Study Endpoints

Primary hypothesis

1. Patients administered solriamfetol will have significantly greater improvements in sleep continuity (total wake time [TWT]) from baseline to post-treatment compared to patients administered placebos. Note: the study is powered for this hypothesis.

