5.6.2 Secondary Study Endpoints

1. Patients treated with CBT-I will have significantly greater improvements in sleep continuity from baseline to post-treatment compared to patients not administered CBT-I.
2. Patients treated with CBT-I in combination with solriamfetol will have significantly greater improvements in sleep continuity from baseline to post-treatment compared to patients treated with CBT-I alone.
3. **Exploratory hypotheses:** Patients treated with CBT-I in combination with solriamfetol will have significantly greater adherence with sleep restriction (i.e., sleep rescheduling, prescribed time to bed [PTTB]) and on daytime performance measures (e.g., ESS, FSS, etc.) compared to CBT-I alone.

i. Primary Safety Endpoints [if applicable]

As noted above, side effects will be assessed in several ways: daily assessments via the sleep diaries, weekly evaluation with a medical symptom checklist (52 symptoms where positive endorsements allow subjects to rate their average severity and number of days affected).

6. Study Population and Duration of Participation

Subjects 25 to 65 years old (inclusive) and who have a stable sleep/wake schedule (no shift work) with a preferred sleep phase between 10:00 PM and 8:00 AM. The recruitment sample will be populated by 40 completed subjects. The study duration will be 12 weeks, with a one-time follow-up at 3 months post-treatment.

a. Inclusion Criteria

Participants will meet the diagnostic criteria for Insomnia Disorder according to Diagnostic and Statistical Manual of Mental Disorders (DSM-5). The complaint of disturbed sleep will meet the following criteria:

- ≥ 30 minutes to fall asleep (SL) and/or ≥ 2 awakenings per night of ≥ 15 minutes duration and/or wake after sleep onset (WASO) time of ≥ 30 minutes where total sleep time (TST) did not exceed 6 hours (unless sleep efficiency [SE] is $\leq 80\%$).
- The problem is present for ≥ 3 nights per week.
- The problem duration exceeds ≥ 6 months.
- The complaint of impaired daytime function must include, although not limited to, the report of daytime fatigue, sleepiness, or both.

Additional inclusion criteria are as follows.

1. Aged 25 to 65 years (inclusive).
2. Have a preferred regular sleep phase between 10:00 PM and 8:00 AM.

b. Exclusion Criteria

Please note that all subjects will have to receive physician assent before being enrolled into the study.

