As noted above, side effects will be assessed in several ways: daily assessments via the sleep diaries and weekly evaluation with a medical symptom checklist (52 symptoms where positive endorsements allow subjects to rate their average severity and number of days affected).

10. Statistical Plan

k. Primary Endpoint

The primary endpoint is total wake time (time spent awake in bed) at the end of post-treatment, as measured via a web based self-report Sleep Diary.

I. Secondary Endpoints

1. Patients treated with CBT-I will have significantly greater improvements in sleep continuity from baseline to post-treatment compared to patients not administered CBT-I.
2. Patients treated with CBT-I in combination with solriamfetol will have significantly greater improvements in sleep continuity from baseline to post-treatment compared to patients treated with CBT-I alone.
3. Exploratory hypotheses: Patients treated with CBT-I in combination with solriamfetol will have significantly greater adherence with sleep restriction (i.e., sleep rescheduling, prescribed time to bed [PTTB]) and on daytime performance measures (e.g., ESS, FSS, etc.) compared to CBT-I alone.

m. Sample Size and Power Determination

To detect a clinically significant difference in self-reported total wake time of 30 minutes between the four treatment groups at the end of post-treatment using an ANOVA test, this study will require 10 subjects per group x 4 groups = 40 treatment completers. These calculations assume a standard deviation in total wake time of 19 minutes, with 80% power to detect the clinically significant change at an alpha level of .05. A total of 60 subjects will be recruited to obtain a sample of 40 subjects that complete the study due to attrition.

n. Statistical Methods

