Primary analyses will be conducted on an intention to treat basis and the trial conducted and reported according to CONSORT guidelines. Variable distributions will be examined to investigate homoscedasticity, outliers and normality, and corrected where appropriate using data transformations. The primary analysis is a 4(condition: +/- solriamfetol and +/- CBT-I) x 2(time: pre- and post-treatment) mixed ANOVA on absolute and percent change in total wake time ([TWT], time spent awake per night). If the interaction between condition and time is significant, Dunnett multiple comparisons will be conducted to further investigate differences in TWT between active treatment conditions versus the control condition to test Hypotheses 1-3. These analyses will be unadjusted in the first instance and then adjusted for covariates (primarily, age and sex).

An interim unadjusted analysis as per above will be conducted after 50% of the target sample have completed post-treatment (i.e., when N=20).

Secondary analyses include examining the interaction between treatment condition and time on other outcomes, including sleep continuity assessed via Sleep Diary (SL, WASO, EMA, TST, SE), insomnia (ISI), daytime sleepiness (ESS and KSS), fatigue (FSS and modified KSS), and daytime function (FOSQ-10, POMS, and PVT). Additionally, compliance to the medication (adherence to daily pill administration, as assessed via blister packs) and to sleep restriction (adherence to prescribed time to bed) will be investigated as covariates.

i. Baseline Data

Baseline and demographic characteristics will be summarized by standard descriptive statistics (including mean and standard deviation for continuous variables such as age and standard percentages for categorical variables such as gender).

ii. Pharmacokinetic Analysis **N/A**

iii. Interim Analysis **N/A**

iv. Safety Analysis

Side effects and adverse events will be assessed in several ways: daily assessments via the sleep diaries, and with a weekly evaluation using a medical symptoms checklist (52 symptoms where positive endorsements allow subjects to rate their average severity and number of days affected),

An adverse event will be defined as 1) any behavioral or health complaint spontaneously reported during the study, 2) an above threshold score on the study clinical assessment instruments (ESS, PHQ-9, or GAD-7), and/or a 20% increase in the medical symptom check list scores (frequency or severity).

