b. Conflict of Interest

All University of Pennsylvania Investigators will follow the University of Pennsylvania Policy on Conflicts of Interest Related to Research.

c. Subject Stipends or Payments

d. Compensation will be pro-rated for each component of the study for a total of \$500 per participant. Specifically, each participant will receive \$50 for completing the screening visit, \$25 for fully completing baseline sleep diaries, \$200 for fully completing all sleep diaries and questionnaires during the treatment period (8 weeks), \$100 for completing the study, and \$125 for completing the follow-up assessment.

k. Publication Plan

While the primary intent of the study is to garner effect size data, if the inferential statistics are significant with 5-8 subjects per condition, the data will be summarized as a short report for the journal SLEEP or the Journal of Sleep Research.

I. References

Relevant references were placed in text (PMID numbers). Also below.

1: 1. Perlis, M., Jungquist, C., Smith, M. T., & Posner, D. (2005). The cognitive behavioral treatment of insomnia: A treatment manual. Springer. ISBN-10: 0387222529, <https://www.amazon.com/Cognitive-Behavioral-Treatment-Insomnia-Session-ebook/dp/B000PC6BGA>

m. Attachments

- Sample Consent Form

a. Source Documents

The data is being acquired on-line. The original questionnaires are not retained, though they can be regenerated from the database data.

b. Case Report Forms (CRFs)

The data is being acquired on-line. The original questionnaires are not retained, though they can be regenerated from the database data.

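### On any reading consistent with the 8-week treatment period, the post-treatment total wake time used for both solriamfetol comparisons contains no active-dose night, and no on-drug contrast is pre-specified

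*Combined protocol and SAP*

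**What the plan says.** **Schedule.** Sections 2, 4 and 6.d describe 8 weeks of capsules: 1 week of placebo run-in, 4 weeks of solriamfetol or placebo, and 3 weeks of placebo run-out. Section 4 ties the first active dose to CBT-I Session 2, which fits a start in week 2. Sections 4 and 6.d add 2 monitored weeks before treatment and 2 after it. Section 4 notes that the group used this design in earlier trials of CBT-I with wake-promoting drugs.

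**Endpoint and tests.** Section 10.k: "The primary endpoint is total wake time (time spent awake in bed) at the end of post-treatment". H1 in Section 5.6 compares improvement in TWT on solriamfetol "from baseline to post-treatment compared to patients administered placebos. Note: the study is powered for this hypothesis". The second secondary hypothesis (Sections 5.6.2 and 10) is that patients given CBT-I "in combination with solriamfetol will have significantly greater improvements in sleep continuity from baseline to post-treatment compared to patients treated with CBT-I alone". The primary model in Section 10.n has two time levels: "2(time: pre- and post-treatment) mixed ANOVA on absolute and percent change in total wake time". Its follow-up comparisons are Dunnett tests of each active condition against control.

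**Nearest text to an on-drug analysis.** Section 4 says that the daily diaries serve to compare conditions and to follow sleep continuity over time. Section 10.n says: "Secondary analyses include examining the interaction between treatment condition and time on other outcomes". Neither names a window inside the active-capsule weeks or a TWT contrast in that window.

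**The concern.** The Introduction sets out to "test whether enhancing daytime wakefulness using a wake-promoting medication, solriamfetol, can improve sleep continuity and daytime performance", and the primary objective (Section 3.1) is the effect of solriamfetol on sleep continuity. A reader would expect at least one planned estimate of TWT while the drug is being taken, and there is none.

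The on-drug effect could go either way. Wake extension may consolidate sleep. Sections 2 and 4 also foresee that an afternoon dose may lengthen sleep latency, which is part of time awake in bed. If an effect in either direction fades once capsules become placebo, the planned test need not show it, and a null H1 would be ambiguous. A later difference remains possible, for example if better adherence to sleep restriction in the combination arm carries forward.

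The Publication Plan states that "the primary intent of the study is to garner effect size data". As written, no on-drug TWT effect size is pre-specified, and a window chosen after unblinding would be post hoc.

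**Working it through.** **1. The plan's own figure.** Section 10.m: 30 min difference, SD 19 min, alpha 0.05, 80% power, four-group ANOVA, 10 completers per group. With least-favourable means 0, 15, 15, 30, the noncentrality is 10 × (15² + 15²)/19² = 10 × 450/361 = 12.5 on 3 and 36 df. Power is 81.1% at 10 per group and 75.8% at 9, so the stated size reproduces. Section 10.m sets its 30 min at post-treatment, so the timing point does not disturb this calculation.

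**2. Day count.** Day 1 is the first run-in day.
- Run-in: days 1-7
- Active: days 8-35 (4 × 7 = 28 nights)
- Run-out: days 36-56
- Post-treatment monitoring: days 57-70

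**3. Candidate windows.** Days since the last active dose = day − 35.

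| Reading of the post-treatment value | Days | Days since last active dose | Active nights |
|---|---|---|---|
| Last day of the 2 monitored weeks | 70 | 35 | 0 |
| Final week of those 2 weeks | 64-70 | 29-35 | 0 |
| All 14 of those nights | 57-70 | 22-35 | 0 |
| Last treatment week | 50-56 | 15-21 | 0 |
| Last two treatment weeks | 43-56 | 8-21 | 0 |

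The wording points to the end of the post-treatment period, so the first two rows fit it best. The documents do not say which nights are averaged.

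**4. Drug clearance.** Section 2.2: "Its elimination half-life is about 7.1 hours". Even the earliest candidate night is 8 × 24/7.1 = 27.0 half-lives after the last active dose. This confirms that the windows are off drug. It says nothing about whether improved sleep persists.

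**5. Precision of an on-drug estimate.** Assume 10 completers per arm, that SD 19 min also holds on drug, no baseline adjustment, and a pooled error on 36 df (t = 2.028).
- Solriamfetol versus placebo, pooled over CBT-I (20 vs 20): SE = 19 × √(1/20 + 1/20) = 6.01; half-width 2.028 × 6.01 = 12.2 min.
- Combination versus CBT-I alone (10 vs 10): SE = 19 × √(2/10) = 8.50; half-width 2.028 × 8.50 = 17.2 min.
- A Dunnett-style comparison of one active arm with control (10 vs 10, critical value about 2.45): 2.45 × 8.50 = 20.8 min.

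All three are below the plan's 30 min difference.

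**6. Diary coverage.** Treatment weeks 4-5 are days 22-35: 14 of 14 nights on active capsules in the solriamfetol arms, and the same length as the 2-week baseline. Diaries are daily, so these nights are already collected.

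**The case against.** The run-out is a deliberate feature with a precedent in the group's earlier trials. The Introduction presents the drug as another route to the mechanism of CBT-I. A common off-drug reading in all four arms, once CBT-I is complete, is a reasonable endpoint for that aim. This stands, and the primary should stay where it is. However, no section says that persistence after stopping is the H1 question.

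The on-drug weeks are also not unobserved. Diaries run daily. Sleep latency and wake after sleep onset are listed outcomes in Section 10.n. The first five participants are enrolled slowly so that longer sleep latency can be noticed, and dose timing may be changed in response. This also stands: the gap is in pre-specification, not in data.

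One reading would put the endpoint on drug, namely taking post-treatment to mean the end of the 4-week active course. The summary table gives 4 weeks of administration, and Section 7.e mentions only 4 weeks of capsules. But Sections 4 and 6.d define treatment as 8 weeks with a separate monitored period afterwards, so this reading has little support. The term itself is never defined.

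A reader might also infer that the trial is underpowered because the effect will have faded. The documents give no persistence figure, so that inference is not supported.

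**Conclusion.** The point holds as a gap in pre-specification. On every reading consistent with the 8-week treatment period, 0 of 28 active-dose nights enter the TWT value used for H1 and for combination versus CBT-I alone. The interval since the last active dose is 29-35 days for a final-week average (35 on the last day, 22-35 for all 14 nights), or 15-21 or 8-21 days if the last one or two treatment weeks are meant. No on-drug TWT contrast is named, so a null H1 would leave no effect and effect only while taken unresolved.

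It does not follow that the primary is wrong, or that an on-drug effect could not be examined at all. Nor can H1 be labelled a persistence estimate until the nights are defined. The day counts rest on the stated schedule alone; the precision figures rest on the assumptions in step 5 of the working. This is a cheap improvement and worth making.

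**What to change.** Leave dosing, schedule, data collection and the post-treatment primary unchanged, and amend the statistical plan as follows.

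1. Define the diary nights that form the post-treatment TWT value, then state the matching estimand. If those nights fall after the last active dose, say that H1 estimates the effect that persists after solriamfetol is stopped.
2. Pre-specify, as a secondary, baseline-adjusted mean nightly diary TWT over a fixed window inside the active-capsule period, for example treatment weeks 4-5. Estimate two contrasts: solriamfetol versus placebo pooled over CBT-I, and combination versus CBT-I alone.
3. State that both are new contrasts outside the Dunnett procedure in Section 10.n, which compares active arms with control only. Place them in the testing order after the primary and the existing secondary hypotheses 1 and 2. Report both estimates with 95% CIs whatever the primary shows.

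The cost is SAP wording and no new data. The downsides are one more pre-specified test family, and a window that falls part-way through CBT-I (5 of 8 weekly sessions by week 5), so it will not show the full CBT-I effect.

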	Inclusion Criteria. Adults ≥ 25 and ≤ 65 years of age with chronic insomnia who meet DSM-5 criteria for Insomnia Disorder and ICSD-3 criteria for Psychophysiological insomnia. In addition, all subjects will have a sleep initiation and/or a sleep maintenance complaint (≥ 30 min. to fall asleep and/or ≥ 30 min. of wakefulness during the night) with a problem frequency ≥ 3 nights/wk and problem duration ≥ 3 mo. This profile must be evident at both intake (based on retrospective reports) and as an average profile from the two weeks of baseline diaries (based on prospective sampling).
	Exclusion Criteria for All Subjects. In brief, the exclusionary criteria are currently in treatment for insomnia, unstable medical or psychiatric illness, night shift work, and/or a history of other sleep disorders.
Investigational Product (drug, biologic, device, etc.)	Solriamfetol (trade name: Sunosi), 75mg.
Duration of administration (if applicable)	4 weeks
Reference therapy	Cognitive Behavioral Therapy for Insomnia (CBT-I)
Statistical Methodology	A 2x2 mixed model design. The two factors will be 1) treatment (+/- solriamfetol and +/- CBT-I) and 2) Time (pre-post assessment, with additional follow-up data).
Safety Evaluations	Daily diary assessments of side effects, weekly symptom checklists to monitor the health status of subjects (upon disbursement of medication). We will utilize a side-effect check list based on the package insert for Solriamfetol.
Data and Safety Monitoring Plan	We will establish a four-person advisory board comprised of a second MD sleep medicine specialist, a clinical psychologist, a nurse sleep scientist, and a biostatistician. Membership consists of persons completely independent of the investigators who have no financial, scientific, or other conflicts of interest with the trial. Collaborators of the PIs will not be eligible to serve on the advisory board. The board will receive reports from the study team every six months with information about the progress of recruitment, the demographic characteristics of participants, serious adverse events, the number of dropouts, and participants' reasons for dropping out, and any protocol amendments. These meetings will focus on the conduct and progress of the study, including participant accrual, protocol compliance, and problems encountered.

BACKGROUND AND STUDY RATIONALE

1. Introduction

Background and Relevant Literature

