Following the intake, all subjects that remain eligible for the proposed study will complete two more assessments prior to being enrolled in the proposed experiment. First, each subject will complete two weeks of daily sleep diaries to confirm 1) their retrospective estimates regarding the type, severity, and frequency of their insomnia and 2) that they are compliant with the daily task of completing the daily diaries. Second, each subject will undergo a Home Sleep Apnea Testing (HSAT, type 3 or 4 sleep study) study to rule out the presence of occult sleep disorders (sleep disorders for which the patient does not exhibit the typical signs and symptoms). This sleep study will be equivalent to the quality of a clinical PSG. These screenings will be conducted according to the Penn CSI Sleep Research Laboratory's standards. The recording montage consists of 14 electrophysiological signals. The basic montage includes 2 EOGs referenced to a single mastoid [LOC & ROC], 6 EEGs referenced to linked mastoids [F3, F4, C3, C4, O1, & O2,], 1 bipolar mentalis EMG, an EKG, 2 bipolar tibial EMGs, a nasal/oral airflow thermocouple, 2 respiratory effort sensors, and an oximeter measure of blood oxygen saturation. All 14 signals will be recorded with SD32 amplifiers and use Sandman v10 acquisition software to transmit data directly to the control room where the PSG can be monitored online and simultaneously recorded to PCs located in the control room. PSG data will be scored according to Rechtschaffen, and Kale's standards and the sleep continuity and sleep architecture variables will be calculated using lab standard definitions. Additionally, AI/AHI indices will be calculated according to AASM criteria. Subjects with an AI (vs. AHI) of >10 will be ineligible for the proposed study.

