o. Subject Population(s) for Analysis

- All-randomized population.
- All-treated population
- Protocol-compliant population

11. Safety and Adverse Events (as stated in the IRB template)

p. Definitions

i. Adverse Event

An adverse event (AE) is any symptom, sign, illness or experience that develops or worsens in severity during the course of the study. Illnesses or injuries will be regarded as adverse events. Abnormal results of diagnostic procedures are considered to be adverse events if the abnormality:

- results in study withdrawal
- is associated with a serious adverse event
- is associated with clinical signs or symptoms
- leads to additional treatment or to further diagnostic tests
- is considered by the investigator to be of clinical significance

ii. Serious Adverse Event

Serious Adverse Event

Adverse events are classified as serious or non-serious. A serious adverse event is any AE that is:

- fatal
- life-threatening
- requires or prolongs hospital stay
- results in persistent or significant disability or incapacity
- a congenital anomaly or birth defect
- an important medical event

Important medical events are those that may not be immediately life threatening but are clearly of major clinical significance. They may jeopardize the subject and may require intervention to prevent one of the other serious outcomes noted above. For example, drug overdose or abuse, a seizure that did not result in in-patient hospitalization, or intensive treatment of bronchospasm in an emergency department would typically be considered serious.

All adverse events that do not meet any of the criteria for serious should be regarded as **non-serious adverse events**.

q. Recording of Adverse Events

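### The primary test compares raw change in total wake time on two unranked scales, without naming the already collected baseline value as a covariate; a lesser gap is intention to treat with no missing-data method

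*Combined protocol and SAP*

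**What the plan says.** Section 10.n (Statistical Methods) gives the primary analysis as four conditions by "2(time: pre- and post-treatment) mixed ANOVA on absolute and percent change in total wake time", with Dunnett comparisons against control if the interaction is significant. On covariates it says: "These analyses will be unadjusted in the first instance and then adjusted for covariates (primarily, age and sex". Neither scale of change is placed ahead of the other.

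The primary hypothesis in section 5.6 is that solriamfetol patients will have "significantly greater improvements in sleep continuity (total wake time [TWT]) from baseline to post-treatment compared to patients administered placebos". Section 10.k defines the endpoint as the TWT level at the end of post-treatment.

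Baseline diary data will exist. Under section 5.1, "each subject will complete two weeks of daily sleep diaries" before enrolment, and the synopsis applies the entry criteria "as an average profile from the two weeks of baseline diaries".

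Section 10.m sizes the trial at 10 completers in each of four groups for a 30-minute difference at alpha .05: "These calculations assume a standard deviation in total wake time of 19 minutes, with 80% power to detect the clinically significant change". It recruits 60 to obtain 40 completers.

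Section 10.n also says "Primary analyses will be conducted on an intention to treat basis", and section 10.o lists an "All-randomized population". No method for missing post-treatment values is given. Section 8.e plans one final visit after early withdrawal, for product collection and adverse-event follow-up.

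**The concern.** There are two main points and one secondary point.

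1. **Baseline is subtracted, not adjusted for.** In a pre/post mixed ANOVA, the condition-by-time F equals the one-way ANOVA F on post minus pre. That fixes the coefficient on baseline at 1. Estimating the coefficient instead gives a residual variance that is never larger, apart from one degree of freedom, and is usually smaller. With 10 per group the difference can matter, and the data needed are already collected.

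2. **Two scales are primary.** If absolute and percent change disagree, no rule says which is the result. Percent change is also one value per subject, so a two-level time factor cannot be applied to it; on that scale the sentence cannot be run as written.

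3. **Secondary: intention to treat has no method behind it.** A classical mixed ANOVA uses only subjects with a post value. If withdrawal depends on arm or early response, randomisation does not protect a completers-only contrast.

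**Working it through.** **Inputs from section 10.m:** 4 groups, n = 10 per group, range of means 30 min, SD 19 min, alpha .05, power 80%.

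**Assumed, not in the documents:** group means 0/15/15/30 min; pre-post correlation r from 0.3 to 0.7; q = SD(pre)/SD(post) from 0.5 to 1.3.

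**Step 1. Reproduce the plan's figure.** One-way ANOVA, noncentrality = n × Σ(group mean − grand mean)² / variance. With means 0/15/15/30 the sum of squares is 225 + 0 + 0 + 225 = 450. At n = 10, 10 × 450 / 361 = 12.47, and power on F(3, 36) is 81.1%. At n = 9 it is 75.8%. So 10 per group reproduces, and 40 / (1 − 1/3) = 60 recruited.

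**Step 2. Variances, with s = SD(post).**
- Change score: (1 + q² − 2rq) s²
- Baseline-adjusted: (1 − r²) s²
- Difference: (q − r)² s², which is never negative and is zero only at q = r.

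**Step 3. Read 19 as the cross-sectional post-treatment SD** (s² = 361). At q = 1:

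| r | Change variance | Change power | Adjusted variance | Adjusted power |
|---|---|---|---|---|
| 0.3 | 1.40 × 361 = 505.4 | 65.3% | 0.91 × 361 = 328.5 | 84.8% |
| 0.5 | 1.00 × 361 = 361.0 | 81.1% | 0.75 × 361 = 270.8 | 91.4% |
| 0.7 | 0.60 × 361 = 216.6 | 96.5% | 0.51 × 361 = 184.1 | 98.4% |

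Adjusted power uses 35 error degrees of freedom instead of 36. Simulation with the slope estimated gives slightly less: 84%, 90–91% and 98%.

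Other values of q, change versus adjusted power:
- q = 0.5: 83.2 v 84.8%, 91.5 v 91.4% (the tie at q = r), 97.7 v 98.4%
- q = 1.3: 50.7 v 84.8%, 65.7 v 91.4%, 86.6 v 98.4%
- Whole grid: change 51–98%, adjusted 85–98%

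**Step 4. Precision for pooled solriamfetol versus placebo (the section 5.6 contrast, 40 subjects).** The 95% half-width is t × 2 × SD / √40. At q = 1 and r = 0.3, change is 2.028 × 2 × 22.48 / 6.325 = 14.4 min, and adjusted is 2.030 × 2 × 18.12 / 6.325 = 11.6 min. At r = 0.5 the pair is 12.2 and 10.6 min; at r = 0.7 it is 9.4 and 8.7 min. Over the grid, change runs from 8.7 to 16.8 min and adjusted from 8.7 to 11.6 min.

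**Step 5. Read 19 as the SD of change.** The planned test then has the 81.1% of step 1. Adjustment at q = 1 gives 94.9%, 91.4% and 87.4% for r = 0.3, 0.5 and 0.7, and 81–99% over the grid.

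**Step 6. Two scales.** Simulation of 40,000 trials per cell, with assumed baseline mean 60 to 120 min, a 30-minute baseline floor suggested by the entry rule, and q and r as above. With no effect, at least one scale is significant in 5.3–6.5% of trials. Under the 0/15/15/30 effect, the two scales disagree on significance in 1–15%.

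**Step 7. Missing data.** The allowance is 20 of 60, but some of that may be lost before randomisation, so loss after randomisation could be anywhere from 0 to 33%. Bias in this trial cannot be sized from the documents. An illustrative simulation with invented, arm-specific withdrawal and a true effect of −5 min gave −8.8 to −9.0 for completers-only ANCOVA, −5.8 to −5.9 for completers-only change, and −4.9 to −5.0 for multiple imputation. This shows only that ANCOVA does not itself repair selective loss.

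**The case against.** The planned test is unbiased under randomisation, matches the wording of improvement from baseline, and the stated sample size reproduces. If 19 is the SD of change, which the last words of the section 10.m sentence allow, the trial has its 80% and adjustment is an efficiency gain. All of that stands.

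The size of the gain rests on r, q and a pattern of means that the documents do not give. At q of 0.5 to 0.6 it is about 0 to 4 percentage points, and the 51% figure is one corner of the grid. This also stands, and the gain must be read as conditional. It does not reverse the choice: the worst case for adjustment is one lost degree of freedom (91.5% against 91.4%).

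The covariate list is open-ended, so baseline TWT is not excluded. But a covariate that is not named in advance, in an analysis that comes second, does not define the primary result. A reader could infer that minutes lead, since the power calculation is in minutes and absolute change is listed first. The false-positive inflation is indeed small; the stronger reason to rank the scales is that a discordant pair has no rule.

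Dunnett comparisons against control do not directly test the pooled solriamfetol hypothesis or combination versus CBT-I alone. That is true, but it is already a feature of the plan and does not bear on whether to adjust for baseline. On missing data, a likelihood-based repeated-measures model could also serve, so the choice of method is open to debate; the absence of any method is not.

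**Conclusion.** The concern holds. The primary test is a raw change-score comparison on two unranked scales, and a collected, relevant baseline measure is not named as a covariate. The cost is precision, not validity, and the stated sample size is not shown to be wrong.

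If 19 minutes is a cross-sectional SD, equal before and after treatment, adjustment adds about 20, 10 and 2 percentage points of power at r = 0.3, 0.5 and 0.7. It adds almost nothing when q is close to r, and more when baseline TWT is the more variable. The two scales raise the false-positive rate only slightly but leave the headline open to choice in an assumed 1–15% of trials. The missing-data gap is real, secondary and cannot be sized. The plan should be changed; confidence is medium because r and q are unknown.

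**What to change.** In section 10.n, make the single primary analysis an ANCOVA of post-treatment diary TWT in minutes, averaged over stated nights, on the four-level condition and baseline diary TWT. Keep the planned Dunnett comparisons. The condition effects are identical to those from an ANCOVA of change with the same covariate, so this serves both the endpoint in section 10.k and the hypothesis in section 5.6. The pooled solriamfetol contrast can be estimated from the same model. Make percent change supportive. The look at N = 20 refers back to the unadjusted analysis, so its wording should be aligned.

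Secondary: include all randomised subjects by one named method, such as multiple imputation under missing at random. Impute post-treatment TWT by sequential regression on condition, baseline TWT, mean TWT in the active-drug weeks and mean TWT in the run-out weeks. Keep the last two as separate predictors, so that the shift off drug is estimated and not carried forward. Report completers as a sensitivity analysis.

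Cost: wording in section 10 and one degree of freedom for the core change, with no new data. Imputation adds modest programming and rests on its assumption. Optionally, diaries could continue after early discontinuation where consent remains; that changes procedures and would need an amendment submitted to the IRB.
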